## **Inclusion Criteria**

1. Adult patients diagnosed with primary and secondary diagnosis of Parkinson's disease
2. Patient 22 years old and older
3. Patients admitted to inpatient units and Center for Ambulatory Surgery
4. Alert and able to follow commands
5. Patient who agree to participate in the study

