## **Secondary Endpoints**

- Difference in scheduled versus actual PD medication administration time
- Number of medication errors

- Number of contraindicated medications administered
- Number of falls
- Number of positive confusion scores
- Number of positive delirium scores
- Length of Stay

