## **Retrospective Study Period**

Version 5 Revised 5/9/2019

Data collection of adult patients admitted with a primary and secondary diagnosis of Parkinson's disease during January – June 2015.

- Data will be extracted from the EPIC (current EMR system at Hackensack University Medical Center).
- Business intelligence will run the data and create reports with the specific data points mentioned above prior to providing it to the study team for further statistical analysis.

Data collected from the automatic dispensing cabinet barcoding database will verify accuracy and timeliness of medication.

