#### **WatchRx System Enrollment:**

Using Internet Explorer web browser, the Principal Investigator and the TC Pharmacist (sub investigator(s) will complete the following:

- Enter the patient's information into the WatchRx Inc. Website interface to create the patient profile and PD medication regimen
- Register the patient into WatchRx web interface via website URL by entering the PD patient's name, unit number and room number.

- Enter the patient PD medication administration schedule as ordered
- Assign the WatchRx Smartwatch to the patient
- Review the WatchRx Smartwatch functions with the patient
- Review the Aware in Care Kit with the PD patient

The primary nurse will be asked to wear the WatchRx smartwatch. After obtaining verbal consent, the Principal Investigator and TC Pharmacist will review the patient's PD medication schedule in WatchRx smartwatch with the primary nurse.

The WatchRx web interface will activate reminder alerts from the patient's WatchRx Smartwatch to the primary nurse WatchRx smartwatch. Alerts reminders will send fifteen minutes before the PD medication is due. Medication reminder alerts will continue to be sent from WatchRx smartwatch worn by the patient to the WatchRx Smartwatch worn by primary nurse at 3-minute intervals for a period of 10 minutes or until the PD medication is administered.

At each end-of-shift and/or at handoff, the WatchRx smartwatch will be cleaned using Super SaniClothTM and the nurses will document completion of the WatchRx smartwatch cleaning procedure on the WatchRx Smartwatch cleaning log and verify by signing their names (Appendix F).

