## **Sample Size Calculation**

A total of 433 patients were admitted to Hackensack University Medical Center with a diagnosis of PD in the year 2014. A convenience sample of 300 patients, 150 patients in the prospective phase and 150 patients in the retrospective phase, and approximately 346 clinicians, before and after implementing the Parkinson's Disease Inpatient Clinical Knowledge and Management education program will be enrolled in the study.

The sample of clinicians will include physician's assistant, advanced practice nurses, staff nurses, nurse educators, case managers, dietitians, pharmacists, physical therapist and occupational therapist. (Table 1)

Categories	Overall population	Sample population	Percentage (Sample size)
Staff Nurses Adult (Inpatient Units)	1931	100	5 %
Nursing Assistants	277	N/A	
Patient Care Technicians	165	N/A	
Advanced Practice Nurses (Adult Inpatient Units)	107	87	81%
Case Managers(Adult Inpatient Units)	48	48	100%
Nurse Educator Adult Inpatient	20	19	95%
Physician's Assistant Adult Inpatient	73	40	54%
Dietitians	17	17	100%
Pharmacists	119	12	11%
Physical Therapist	17	17	100%
Occupational Therapists	6	6	100%

Table 1

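### Ambulatory-surgery and inpatient-unit patients are pooled, with no shared setting rule for the 2015 and prospective cohorts, so a difference in case mix could pass for an effect on length of stay.

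*Combined protocol and SAP*

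**What the plan says.** **Eligibility.** The third inclusion criterion covers "Patients admitted to inpatient units and Center for Ambulatory Surgery". The first requires the diagnosis: "Adult patients diagnosed with primary and secondary diagnosis of Parkinson's disease". None of the five inclusion and five exclusion criteria asks for a minimum stay, an ordered PD drug or a dose due during the stay.

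**The 2015 cohort.** The Retrospective Study Period section reads: "Data collection of adult patients admitted with a primary and secondary diagnosis of Parkinson's disease during January – June 2015". It neither includes nor excludes the Center for Ambulatory Surgery (CAS).

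**Endpoints.** Among the Secondary Endpoints are "Difference in scheduled versus actual PD medication administration time", "Length of Stay", and numbers of falls, medication errors, contraindicated drugs given, and positive confusion and delirium scores. No endpoint is limited to a care setting.

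**Sample.** The Sample Size Calculation section states "A convenience sample of 300 patients, 150 patients in the prospective phase and 150 patients in the retrospective phase". It gives no quota, matching or stratification by setting.

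**Analysis.** The Data Analysis section names two-sided t or Wilcoxon rank sum tests for continuous variables and Fisher's exact or chi-square tests for categorical ones. It plans no adjustment, stratification or subgroup by setting.

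**Recording of setting.** The Measurements list does not name care setting. The WatchRx set-up records a unit number, but only for prospective patients. The same set-up includes the step "Enter the patient PD medication administration schedule as ordered".

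**The concern.** An ambulatory-surgery visit is usually much shorter than a stay on an inpatient unit. That is an inference, since the protocol does not describe CAS stays. If it is right, pooled length of stay is a mixture of two distributions, and its mean depends on the share of CAS patients. Prospective CAS patients are eligible by name, whereas whether the 2015 extract contains them depends on how the report is built. Nothing in the plan keeps the two shares equal, and nothing in the analysis would reveal that they differ.

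At stake is the reading of the patient-level hypotheses (Ho2 and Ho3). A shorter mean stay after the Program and the watch could reflect case mix alone. Falls, medication errors and positive scores are stated as numbers with no time denominator, so they would move the same way.

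The timing endpoint raises a separate, smaller matter. Scheduled-versus-actual time is undefined for a patient with no scheduled PD dose, and the plan does not say which patients form that analysis set.

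**Working it through.** **The plan's own figure.** The patient total is 150 + 150 = 300, which agrees. No alpha, power, effect or SD is given, so there is no sample-size calculation to reproduce.

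**Room for selection.** The plan states "A total of 433 patients were admitted to Hackensack University Medical Center with a diagnosis of PD in the year 2014". Half a year at that rate is 433 / 2 = 216.5, and 150 / 216.5 = 69%. If 2015 resembled 2014, the retrospective 150 would be a subset of those admitted, and the rule for choosing it is not given.

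**Inputs for length of stay**
- From the documents: 150 per phase; two-sided, unadjusted test.
- Assumed: alpha 0.05; inpatient stay mean 6, SD 5 days; CAS stay 0 days; CAS share 0% in 2015 and p in the prospective phase; no true effect.

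**Formulas (normal approximation)**
- Prospective mean = 6(1 − p)
- Prospective variance = (1 − p)(25 + 36) − mean²
- SE = √[(25 + prospective variance) / 150]
- k = (6 − mean) / SE
- P(reject) = 1 − Φ(1.96 − k) + Φ(−1.96 − k)

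| p | Mean | Variance | SE | Spurious difference (days) | k | P(reject) |
|---|---|---|---|---|---|---|
| 0% | 6.0 | 25.00 | 0.577 | 0 | 0 | 0.050 |
| 5% | 5.7 | 25.46 | 0.580 | −0.3 | 0.517 | 0.081 |
| 10% | 5.4 | 25.74 | 0.582 | −0.6 | 1.032 | 0.178 |
| 20% | 4.8 | 25.76 | 0.582 | −1.2 | 2.063 | 0.541 |

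**Sensitivity to the assumed stays.** With inpatient mean/SD of 4/3, 5/4 or 7/6 days and a CAS stay of 0.5 day (SD 0.25), still with 0% CAS in 2015:
- 10% prospective share: difference −0.35 to −0.65 day, false rejection 16–17%.
- 20% prospective share: difference −0.70 to −1.30 days, false rejection 47–52%.

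**Sensitivity to the shares.** Under these alternative inputs, 10% in 2015 against 20% prospectively gives 16–17%. Reversing the shares gives the same rate with the opposite sign. With 10% in both phases, the difference is 0 and the rate is 5%.

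**Wilcoxon test.** The plan allows it for non-normal data, and stay is usually skewed. If every CAS stay ranks below every inpatient stay and 2015 has none, the probability that a prospective stay exceeds a 2015 stay is (1 − p)/2, a shift of p/2 from one half. The null SE is √[301 / (12 × 150 × 150)] = 0.0334. For p = 5%, 10% and 20%, k = 0.75, 1.50 and 2.99, and false rejection is about 12%, 32% and 85%. Simulation with gamma-distributed stays gives about 12%, 32% and 86%. This result does not depend on the assumed mean or SD, only on the ranking and the shares.

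**Timing endpoint.** Suppose a share q of each phase has no scheduled dose. For q = 10%, 20% and 30%, evaluable patients per phase are 150(1 − q) = 135, 120 and 105. The difference detectable with 80% power at 150 per phase is (1.960 + 0.842)√(2/150) = 0.323 SD. Power for that difference falls to 76%, 71% and 65%. The documents do not give q.

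**The case against.** **CAS inclusion looks deliberate.** The Target Audience list in Appendix B names CAS among the units whose registered nurses are to be trained, and the secondary objectives speak of PD patients generally. CAS patients can also receive a contraindicated drug during a short stay. A reader might infer that CAS patients should be ineligible. The documents do not support that, because removing them would change the intended population. This stands, and it argues for separate reporting. It does not justify pooling CAS into length of stay.

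**No imbalance is shown.** A reader might take the 2015 cohort to contain no CAS patients. It is described only as admitted, the verb that criterion 3 also uses for CAS. Neither the direction nor the size of an imbalance can be read from the documents, and equal shares would do no harm. This stands too. What remains is that nothing secures equality and setting is not a listed measurement for both phases.

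**Patients without a scheduled dose.** A reader might infer that such patients will be given a watch with nothing to prompt, or that every CAS patient lacks a timing value. In the enrollment procedure, medication reconciliation comes first, and the set-up lists entry of the ordered schedule ahead of assigning the watch, so these patients may be filtered out in practice. Nothing equates CAS patients with no-dose patients. However, such a filter would act in the prospective phase only, which is a reason to state the timing set for both.

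**A dose requirement at entry could itself bias the comparison.** A 2015 patient whose home PD drug was never ordered may be a medication error, which is an endpoint. Excluding that patient would remove poor baseline cases, while study-led reconciliation could keep the comparable prospective patient in. This stands and shapes the remedy.

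**Scope.** The primary endpoint is the clinician knowledge score, which is untouched. CAS mix is also only one of several differences between a consented, alert, watch-wearing cohort and a chart-review cohort, and equalising it leaves the others.

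**Conclusion.** The point holds as a gap in the definition of cohorts and analysis sets for secondary endpoints. The setting rule is explicit in the inclusion criteria and absent from the 2015 cohort definition, and the pooled unadjusted tests cannot separate case mix from effect.

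Under the main assumptions, false rejection for length of stay is about 8%, 18% and 54% at prospective CAS shares of 5%, 10% and 20% against none in 2015, and 5% at equal shares. These figures illustrate sensitivity and do not estimate the bias in this study. They rest on assumed stays, assumed shares and the inference that CAS stays are short. The conclusion goes no further than this: the plan leaves length of stay, and counts that accrue with time in hospital, open to a difference in setting mix. It does not show that a mismatch exists or which way it would run.

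**What to change.** 1. Keep CAS eligible if that is intended, but apply one EPIC encounter-type definition to the 2015 extract and the prospective cohort, and state how the 150 retrospective patients are chosen.
2. Add care setting to the Measurements list for both phases and report the CAS share by phase.
3. Compare length of stay, and counts that accrue with time in hospital, among inpatient-unit patients only or stratified by setting. Report CAS patients separately.
4. Define the scheduled-versus-actual timing analysis set, identically in both phases, as patients with at least one scheduled PD dose, and report how many patients this leaves out. Do not make an ordered dose an entry criterion, because an omitted PD order may itself be a medication error.

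**Cost.** A few lines of protocol text and an encounter-type and order flag in the EPIC extract, which already supplies data for both phases. The sample for length of stay and timing becomes somewhat smaller: at an assumed 10% share left out, 135 rather than 150 per phase. Keeping 150 evaluable would need 150 / 0.9, or 167 per phase.

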## **Exclusion Criteria**

1. Patients less than or equal to 21 years of age
2. Patients who refuse or unable to wear the WatchRx smartwatch
3. Disoriented and unable to follow commands
4. Patients who are allergic to silicone, stainless steel and/or latex
5. Patients positive for Clostridium difficile and/or Candida auris

## **Study Period**

**Retrospective Data Period:** January 2015 – June 2015

**Prospective Data Period:** After the clinicians have completed the Parkinson's Disease Inpatient Clinical Knowledge and Management Program and the WatchRx Smartwatch is integrated within medication administration for PD medications

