While the goal during hospitalization is to provide, safe and effective high quality care. 74% of PD patients receive incorrect medications (Martinez-Ramirez et al, 2015 and are at increased risk for developing complications related to medication administration. According to the Institute for Safe Medication Practices [ISMP] (2015 p. 19) “patients with PD require strict adherence to an individualized timed medication regimen of anti-parkinsonian agents.” Medications must be administered on time, based on the patient’s unique schedule. A comprehensive search of the literature from 2009 – 2015 found few studies evaluating the impact of focused integrated inter and multidisciplinary approach to managing PD patients during hospitalization. In another survey, PD patients’ perceptions is that hospital staff lacked understanding of PD, the importance of medication timeliness, and appreciation of valuable insights from patients, families and caregivers (Oguh & Videnovic, 2012).

A paradox of the U. S. healthcare system is that it leads the world in medical science and technology, yet there is limited application of technology to enhance patient-centered care in the hospital setting. In accordance with the Institute of Medicine’s (2001) quality performance goals, safety, effectiveness, timeliness, patient-centeredness, efficacy and equity, this study will integrate WatchRx system, a medication reminder system. The WatchRx system includes a

smartwatch, caregiver app and online web interface which allows clinicians to customize the medication administration time and alerts the patient and the nurse when the medication to be administered.

This study will conduct research on establishing multidisciplinary clinical guidelines in management of PD across the acute care setting. We will further explore the impact of PD medication management on patients hospital length of stay and complications associated with mismanagement. We intend to create a PD registry for Hackensack University Medical Center, and possibly expand across the Hackensack Meridian Health Network in the future. According to the New Jersey Assembly Bill 2955, December 2014, patients and/or their designated caregiver must receive discharge instructions prior to discharge from the hospital and appropriate referrals for follow-up care. This study aligns New Jersey Bill 2955 (2014) mandating the education and preparation of designated caregiver in the discharge plan of care of hospitalized PD patients.

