## **Hypothesis**

Ho1:

Parkinson's Disease Inpatient Clinical Knowledge and Management Program will not make a difference in the clinician knowledge.

Ha1:

Parkinson's Disease Inpatient Clinical Knowledge and Management Program will make a difference in the clinician knowledge.

Parkinson's Disease Inpatient Clinical Knowledge and Management Program will not make a difference in the customized PD order time and PD medication administration time, complications (administered contraindicated medication, falls, positive delirium scores, and positive confusion), medication error and length of stay during hospitalization.

Ha2:

Parkinson's Disease Inpatient Clinical Knowledge and Management Program will make a difference in the customized PD order time and PD medication administration time, complications (administered contraindicated medication, falls, positive delirium scores, and positive confusion), medication error and length of stay during hospitalization.

Ho3:

WatchRx System will not make a difference in the customized PD order time and PD medication administration time, complications (administered contraindicated medication, falls, positive delirium scores, and positive confusion), medication error and length of stay during hospitalization.

Ha3:

WatchRx System will make a difference in the customized PD order time and PD medication administration time, complications (administered contraindicated medication, falls, positive

delirium scores, and positive confusion), medication error and length of stay during hospitalization.

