## **Secondary Objectives**

1. To measure the difference that the Parkinson's Disease Inpatient Clinical Knowledge and Management Program has on PD medication administration time, administered contraindicated medication, PD medication errors, falls, positive confusion, positive delirium scores, and length of stay for PD patients.
2. To measure the difference that the WatchRx system has on PD medication administration time, administered contraindicated medication, PD medication errors, falls, positive confusion, positive delirium scores, and length of stay for PD patients.

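### The Program and WatchRx hypotheses (Ho2, Ho3) cannot be tested separately, because patients are planned to receive either neither component or both

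*Combined protocol and SAP*

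**What the plan says.** The Hypothesis section gives each component its own null hypothesis on the same patient outcomes. Ho2 concerns the education Program. Ho3 reads "WatchRx System will not make a difference in the customized PD order time" and continues through the same list. Secondary Objectives repeats the split: objective 1 concerns the Program, and objective 2 is "To measure the difference that the WatchRx system has on PD medication administration time" and the remaining outcomes.

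Sample Size Calculation defines the patients: "A convenience sample of 300 patients, 150 patients in the prospective phase and 150 patients in the retrospective phase". Study Period fixes the retrospective group as January to June 2015. It opens the prospective period once clinicians have finished the Program "and the WatchRx Smartwatch is integrated within medication administration for PD medications". The synopsis says the same.

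Three further provisions settle exposure within the prospective group:

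- Exclusion Criteria removes "Patients who refuse or unable to wear the WatchRx smartwatch".
- WatchRx System Enrollment includes the step "Assign the WatchRx Smartwatch to the patient".
- Prospective Study Period lists WatchRx web records as a data source.

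Data Analysis offers generic tests for independent groups and does not map any of them to Ho2 or Ho3. Limitations names only the single site and the convenience sample.

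**The concern.** Two effects on one outcome can be told apart only if some patients receive one component without the other. The plan describes no such patients: there is no Program-only, watch-only, staggered or concurrent control group. One before/after difference would have to serve as the evidence for two separate causal claims.

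Two of the three hypotheses and both secondary objectives depend on this. A report that the watch alone, or education alone, changed falls, medication errors or length of stay would have no support in the data.

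The single contrast that remains has its own weaknesses. It compares different calendar periods. It also compares patients selected by consent ("Patient who agree to participate in the study") and by willingness and ability to wear the watch with 2015 records, to which neither filter can apply. Limitations does not warn the reader of any of this.

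**Working it through.** **The plan's own figure.** 150 + 150 = 300, as stated. It is described as a convenience sample, and no alpha, power, effect size or standard deviation is given, so there is no power calculation to reproduce. The question is one of identifiability.

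**Inputs.**

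| Group | n | Program | WatchRx | Source |
|---|---|---|---|---|
| Retrospective, January–June 2015 | 150 | 0 | 0 | Study Period; Sample Size Calculation |
| Prospective | 150 | 1 | 1 | Study Period; Exclusion Criteria; WatchRx System Enrollment |

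The zeros for 2015 are inferred. Study Purpose and Rationale says "this study will integrate WatchRx system, a medication reminder system", which is prospective wording, and the prospective period is defined by both components being in place. The ones describe what is assigned, not which alerts were delivered.

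**Step 1: the model implied by Ho2 and Ho3.** Mean outcome = a + b·Program + c·WatchRx.

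- Retrospective mean = a.
- Prospective mean = a + b + c.
- Difference D = b + c.

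There are two means and three unknowns. Over the 300 rows, the matrix [1, Program, WatchRx] has rank 2 of 3, and the two exposure columns have correlation 1.0. Neither b nor c is estimable; b + c is.

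**Step 2: what this means for a result.** Take an illustrative baseline of 20 and D = −10 (assumed values).

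| b (Program) | c (WatchRx) | Retrospective mean | Prospective mean |
|---|---|---|---|
| −10 | 0 | 20 | 20 − 10 + 0 = 10 |
| 0 | −10 | 20 | 20 + 0 − 10 = 10 |
| −20 | +10 | 20 | 20 − 20 + 10 = 10 |

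All three fit identically, and in the third the watch does harm. Adding patients to the same two groups leaves the rank at 2.

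**Step 3: calendar period.** A period indicator is again 0 for the first 150 and 1 for the second 150. The matrix [1, Program, WatchRx, period] has rank 2 of 4, so b + c is also inseparable from any change over time. The length of the gap cannot be stated because no prospective start date is given.

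**Step 4: the merged contrast.** The matrix [1, prospective] has rank 2 of 2. One combined before/after difference is estimable.

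**Step 5: would a Program-only group rescue the split?**

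- *Sequential group* (Program first, watch later). Rank is 3 of 3 if time effects are ignored, but 3 of 5 if each later group has its own period effect. Time confounding remains.
- *Concurrent group* sharing one prospective period. [1, Program, WatchRx, period] has rank 3 of 4. WatchRx becomes estimable; the Program does not, because it still coincides with the move from 2015 to the prospective period.

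The precision cost of the concurrent option can be sketched by assuming a 75/75 split of the prospective patients, two-sided alpha 0.05 and 80% power. The detectable standardised difference is (1.960 + 0.842) × √(1/n₁ + 1/n₂):

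- 150 versus 150: 2.802 × √(2/150) = 0.323.
- 75 versus 75: 2.802 × √(2/75) = 0.457.

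Power of the 75 versus 75 comparison at a difference of 0.3235 SD is about 51%.

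**The case against.** The strongest reply is that delivered exposure may vary even though assigned exposure does not. The primary nurse is asked to wear a watch and gives verbal consent, so alerts may not reach a wearing nurse for every patient. Table 1 samples 100 of 1,931 staff nurses for the knowledge assessment, so staff training may also be uneven. This limits the rank result to assignment. It does not rescue Ho2 and Ho3: the plan specifies no delivery-based analysis, and one would compare self-selected subgroups.

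Second, Prospective Study Period dates data collection from Program completion without naming the watch, and Data Analysis allows ANOVA or Kruskal-Wallis with pairwise tests, which could suggest a third group. Neither section defines a Program-only cohort. Study Period requires both components, and the multi-group tests could equally serve the clinician roles.

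Third, the plan never says how Ho2 and Ho3 would be tested, so double attribution is an inference. That is fair, but no test on these two groups could separate them.

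Fourth, a concurrent Program-only group could keep the WatchRx question alive. That is true if enrolment allows it, but it is a redesign with a new allocation and smaller groups, not a correction to the present plan.

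Finally, the primary objective is untouched and the study describes itself as quasi-experimental. That limits the reach of the problem, but two formal hypotheses still cannot be answered as written.

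**Conclusion.** The concern holds, with high confidence. As assigned, Program and WatchRx exposure are the same variable in all 300 patients. Ho2 and Ho3 therefore reduce to one comparison per endpoint (rank 2 of 3), and that comparison is inseparable from calendar period (rank 2 of 4) and from prospective-only consent and watch-wearing.

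The conclusion rests on two readings: that the 2015 patients had neither component, and that every prospective enrollee is assigned a watch after the Program is complete. Both fit the text, although the first is not stated outright. The ranks show that the split is impossible; they do not measure the size of any bias.

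Other elements of the prospective package, such as the PD registry, investigator and pharmacist reconciliation and the Aware in Care Kit, may also contribute to the difference. The documents do not establish how far these reached every prospective patient or were absent in 2015.

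This must be corrected because it decides what the study can conclude about patient outcomes.

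**What to change.** 1. **Synopsis, Hypothesis and Secondary Objectives:** replace Ho2 and Ho3 with one hypothesis, and objectives 1 and 2 with one objective, comparing the combined prospective package with January to June 2015 care. The Research Question already names the Program and WatchRx together.
2. **Data Analysis:** name prospective versus retrospective as the single patient contrast, and state that no effect will be attributed to the Program or to WatchRx alone.
3. **Limitations:** add that the components are not separable, and that the contrast is confounded with calendar period and with consent and watch-wearing requirements that apply only prospectively.
4. **If a Program-only interval exists:** define its dates and patients, and report it as exploratory and still confounded with time.

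The cost is text edits, with no new data collection. The study gives up its component-specific patient-outcome questions, which its two groups cannot answer. If the sponsor wants to keep the WatchRx question and enrolment permits, a concurrent Program-only group would be needed. That is a larger change, with the loss of precision shown above, and it would still leave the Program effect confounded with time.
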